11.4.7 Columbia-Suicide Severity Rating Scale

With global amendment 6 to the protocol, the Columbia-Suicide Severity Rating Scale (C-SSRS) was added as an assessment at all study visits. Specific rules are provided to the study sites with regard to the identification of AEs or SAEs based on the outcome of this assessment. Because clinical events of interest will be recorded as AEs or SAEs, no study variable is defined for this assessment and no analyses are planned for the C-SSRS within the context of this study. However, subject data listings of the data for the C-SSRS will be provided. Additional listings will be provided for the subset of subjects with suicidal ideation and the subset of subject with actual suicide attempts.

Suicide ideation includes a “yes” answer to any 1 of the 5 suicidal ideation questions:

- [REDACTED]
- [REDACTED]
- [REDACTED]
- [REDACTED]
- [REDACTED]

Suicide attempt includes response of a “yes” answer to any 1 of the 3 suicide attempt questions:

- [REDACTED]
- [REDACTED]
- [REDACTED]

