- (k) Procedures only performed during the first 2 years of -subject participation in the study (eg, until last scheduled visit [Y3-YEV]) or EDV/FV in case the subject discontinues participation within the first 2 years).
- (l) The C-SSRS assessment will be implemented by site per IRB/IEC approval and upon completion of required training. As of the time of Protocol Amendment 6, all subjects had completed their Entry Visit. Thus, the C-SSRS was not assessed for any subjects at their Entry Visit.
- (m) For subjects that may transition to another BRV study or a managed access program or similar type of program, the EDV will need to be completed, however down-titration and FV may not be applicable.

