#### **14.2 Subject Information and Consent**

The original Informed Consent form can be amended as appropriate. If the Informed Consent form is amended during the study, the Investigator (or the Sponsor, if applicable) must follow all applicable regulatory requirements pertaining to the approval of the amended Informed Consent form by the IRB/IEC and use of the amended form.

All studies conducted at centers in the United States must include the use of a Health Insurance Portability and Accountability Act Authorization form.

Adequate information will be provided to the subject in both oral and written form and consent will be obtained in writing prior to performance of any study specific procedure. The content and process of obtaining informed consent will be in accordance with all applicable regulatory and IEC/IRB requirements.

For subjects already ongoing in the study, a new informed consent will be issued and need to be signed covering the increased risk of suicidality or suicidal thoughts to comply with the warning issued by the FDA subsequent to analysis performed on marketed anti-epileptic drugs. Although data from BRV studies were not included in FDA's analysis, this risk may be expected because BRV belongs to this class of medication.

The Sponsor may provide a sample informed consent form and a subject information sheet. The final consent form must be approved by the IEC/IRB and should contain the applicable ICH-GCP elements in a language readily understood by the subject (i.e., lay terminology).

The Investigator, or a person designated by the Investigator, should fully inform the subject about all pertinent aspects of the study including the fact that the protocol has been granted the approval of the IRB/IEC and local regulatory authorities if required.

Subjects will be informed of the purpose of the study in unambiguous language they easily understand. Their participation is voluntary and they can at any time decide to stop their participation without any influence on their future care or treatment. The subjects must be informed about the main procedures used to guarantee their anonymity, especially during the analysis of their personal data. They will receive complete written information in the Subject Information Sheet. Subjects should be able to ask any questions about the study and to receive relevant answers.

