11.2.2 General summaries of TEAEs

Pre-treatment AEs will be provided in a subject data listing; no summaries of pre-treatment AEs are planned.

An overall summary of AEs will provide the overall number of TEAEs and the numbers and percentages of subjects with at least 1 TEAE, with a TEAE that led to permanent discontinuation of study drug, with a drug-related TEAE, with a severe TEAE, with a treatment-emergent SAE, and with a drug-related treatment-emergent SAE. The number and percentage of subjects who died will also be summarized. This summary will be provided for all subjects in the Safety Analysis Set and also by subgroup for geographic region and seizure type.

The following summaries of TEAEs will be provided by MedDRA SOC and PT. All summaries are for the combined Evaluation, Down-Titration, and Post-Treatment Periods unless otherwise indicated.

Overall Incidence Summaries

- Incidence of TEAEs
- Incidence of TEAEs by 3-month time interval
- Incidence of TEAEs by study period (Evaluation, Down-Titration, Post-Treatment)
- Incidence of TEAEs for TEAEs occurring in at least 5% of subjects
- Incidence of TEAEs by 3-month time intervals for TEAEs occurring in at least 5% of subjects overall
- Incidence of non-serious TEAEs occurring in at least 5% of subjects

The incidence of TEAEs occurring in at least 5% of subjects will be summarized overall as noted above and also by subgroup for geographic region, seizure type, and randomized treatment from the previous double-blind study.

A subject is included in a 3-month interval if the subject was receiving BRV at any time during that interval based on their duration of exposure to BRV (eg, a subject with exposure for 91 days is included in the time interval for Months 1-3 and Months 4-6). Summaries of AEs by 3-month intervals will include all subjects who are classified into each time interval

as defined above. TEAEs which had onset prior to or on the date of the last dose of BRV are included in summaries by 3-month time intervals.

Maximum Intensity and Causality

- Incidence of TEAEs by maximum intensity
- Incidence of drug-related TEAEs

Serious Adverse Events

- Incidence of treatment-emergent SAEs

Discontinuations due to TEAE

- Incidence of TEAEs leading to permanent discontinuation of study drug

TEAEs of interest

AEs of interest will be identified based on MedDRA search criteria, which are documented outside of the SAP. The following summaries will be provided for AEs of interest:

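### C-SSRS began mid-study and feeds the AE tables without a summary of its own, so the suicidality TEAE time trend is confounded with the change in ascertainment

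*SAP*

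**What the plan says.** **Introduction of the scale.** SAP 11.4.7: "With global amendment 6 to the protocol, the Columbia-Suicide Severity Rating Scale (C-SSRS) was added as an assessment at all study visits". Protocol 5.1, Table 5:1 footnote (l): "The C-SSRS assessment will be implemented by site per IRB/IEC approval and upon completion of required training". The same footnote records that all subjects were by then past entry: "Thus, the C-SSRS was not assessed for any subjects at their Entry Visit".

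**Use of the findings.** SAP 11.4.7: "Specific rules are provided to the study sites with regard to the identification of AEs or SAEs based on the outcome of this assessment". The rules are not reproduced in the SAP. Because clinical events will already be recorded as AEs or SAEs, the SAP concludes that "no study variable is defined for this assessment and no analyses are planned for the C-SSRS within the context of this study". It plans a listing of all C-SSRS data and two subset listings, for ideation and for attempts.

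**AE tables.** SAP 11.2.2 tabulates TEAEs overall and gives "Incidence of TEAEs by 3-month time interval". AEs of interest get the same treatment, but their search criteria are kept outside the SAP. Intervals count from first BRV dose (SAP 3.2.5). An AE is treatment-emergent according to its onset date (SAP 11.2.1).

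**Versions of the scale.** Protocol 9.3.1 uses an Already Enrolled Subjects version, which looks back both before entry and since study start, and a Since Last Visit version. Some answers on either version lead to withdrawal.

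**Status of the risk.** Protocol 14.2 requires subjects already in the study to sign a new consent "covering the increased risk of suicidality or suicidal thoughts".

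**The concern.** The SAP's reason for not analysing the C-SSRS is that its findings will appear as AEs. That step merges two ways of finding events. Before a site started the scale, suicidality reached the database through spontaneous report, a general health question, diary review and the psychiatric part of the neurological examination. Afterwards, trained staff asked about it directly at most visits.

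Nobody had the scale at entry, so the share of subject-time under structured questioning starts near zero and tends to rise with time since first dose. That is also the axis of the 3-month tables. A rising suicidality rate could therefore reflect longer exposure, more systematic asking, or both, and no planned summary tells them apart. Nor does any planned summary say how many subjects were ever asked. The overall percentage uses the Safety Analysis Set, which includes anyone who left before roll-out.

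This bears on the primary objective, which is long-term safety, and on the TEAE and SAE variables that serve it. No other summarised instrument can check a late trend. HADS is summarised for the first 2 years only and excludes N01193 subjects (SAP 11.4.6). Psychiatric and mental status is only listed (SAP 11.4.5).

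**Working it through.** The plan states no suicidality rate, date for Amendment 6 or capture rate, so there is no figure to reproduce. The check has two parts.

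**1. Is the confounding built in?**
- No subject was assessed at entry (Protocol 5.1, footnote (l)), so every subject has some follow-up without the scale.
- Roll-out was by site, so there is no single switch date.
- The table axis is days from first dose, not calendar time (SAP 3.2.5). A staggered start gives a gradual drift rather than a step.
- No table in SAP 11.2.2 or 11.4.7 divides events or exposure at the start of the scale.

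The structure is therefore confirmed from the documents.

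**2. How large could the effect be?** Let the reported risk in interval j be

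reported = true × [(1 − s) × c + s],

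where s is the share of subject-time in that interval after C-SSRS start, and c is the share of true events captured without C-SSRS (taken as 1 with it). All inputs are assumptions: a flat true risk of 0.5% per 3-month interval; c from 0.25 to 1; and a lag from first dose to first C-SSRS spread uniformly over 1–24, 12–60 or 24–84 months.

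Worked case, c = 0.5 and lag 12–60 months:
- Months 1–3: s = 0, so reported = 0.5% × 0.5 = 0.25%.
- Months 22–24: s = (22.5 − 12)/48 = 0.219, so reported = 0.5% × (0.781 × 0.5 + 0.219) = 0.305%.
- Months 82–84: s = 1, so reported = 0.5%. The ratio to Months 1–3 is 2.0.

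Ratio of Months 82–84 to Months 1–3 with a flat true risk:

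| c | lag 1–24 | lag 12–60 | lag 24–84 |
|---|---|---|---|
| 0.25 | 3.68 | 4.00 | 3.93 |
| 0.50 | 1.95 | 2.00 | 1.98 |
| 0.75 | 1.32 | 1.33 | 1.33 |
| 1.00 | 1.00 | 1.00 | 1.00 |

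*A true trend is distorted, not erased.* With c = 0.5 and lag 12–60 months, compare Months 58–60 with Months 1–3. If true risk halves every 24 months, the true ratio is 0.19 and the reported ratio 0.38. If it doubles every 24 months, they are 5.19 and 10.21.

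*Look-back reduces the effect.* Suppose the first C-SSRS recovers a fraction f of missed earlier events among the proportion p still on study, and these are dated by onset. Early capture becomes c + (1 − c) × f × p. With c = 0.5:
- f = 0.5, p = 1: 0.75, ratio 1/0.75 = 1.33.
- f = 0.5, p = 0.5: 0.625, ratio 1.6.
- f = 1, p = 1: 1.0, ratio 1.0.

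The model leaves out withdrawals triggered by the scale. These remove higher-risk subjects from later intervals and push the other way, so the model cannot show a reversal even though one is possible.

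**The case against.** A fair defence has several parts.

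- **Early intervals can contain solicited events.** A reader might infer that structured questioning shows only in later exposure. The documents do not support that. The Already Enrolled Subjects version asks about the time since study start, and TEAEs are placed by onset, so events found at the first C-SSRS can fall in Months 1–3. This stands and limits the claim.
- **Earlier ascertainment was more than spontaneous report.** A general prompt was always used (Protocol 12.1.2). Daily record cards asked for unusual health events (11.1.13). Psychiatric symptoms were recorded as present or absent (11.1.11), and most subjects completed HADS during the first 2 years. None of this replaces direct questioning about suicidality, but it makes a very low capture rate less certain.
- **Listings are planned.** With few events, a reader could rebuild each subject's first C-SSRS date and the number assessed. That is true, but listings give no denominators or rates, and the 3-month table will be read without them.
- **Some safeguards exist.** Events with onset before first dose are not TEAEs, apart from the incomplete-date rule in SAP 11.2.1. Interval denominators count only subjects on BRV in that interval, so the denominator complaint applies to overall incidence only.
- **The SAP matches the protocol.** No C-SSRS variable is listed in Protocol 13.1.2, and the study is descriptive. This explains the choice but does not separate the two sources.
- **A split by onset date alone would fail.** It would put look-back events in the earlier period. This is right, and the fix allows for it.

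A term list for suicidality may already exist among the AE-of-interest criteria; the documents do not show it.

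**Conclusion.** The point holds as one of confounding. Suicidality TEAE incidence pools events found with and without structured questioning, and the 3-month trend is tied to the start of the C-SSRS and may be inflated by it.

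A reader might go further and call the trend an artefact. The documents do not support that. They give no amendment date, lag to first assessment or capture rate, and a real trend would still show through.

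Size and direction are undetermined. The illustrative range is from no distortion (complete capture without the scale, or full look-back recovery with everyone still on study) to about fourfold (a quarter captured, no look-back recovery). Onset-dated look-back answers reduce the effect, and C-SSRS-triggered withdrawals may reduce or reverse it. This uncertainty is the reason to show the two sources apart. The matter is a worthwhile, inexpensive improvement to reporting; it does not invalidate the safety analysis.

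**What to change.** Amend SAP 11.4.7 and the related AE outputs as follows.

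1. **C-SSRS count table.** Report subjects with ideation and subjects with attempts, with subjects having at least one C-SSRS as the denominator. Show Since Last Visit answers separately from Already Enrolled Subjects look-back answers. Where possible, divide the look-back answers into before entry and since study start.
2. **Suicidality TEAE table.** For a fixed list of preferred terms, report subjects with TEAEs and subject-years before and after each subject's first C-SSRS. Give a separate row to events first identified by the look-back assessment (onset before, detection at or after, the first C-SSRS) and do not count them as earlier-period events.
3. **Footnote to the 3-month TEAE tables.** State that ascertainment of suicidality changed during the study, on dates that vary by site. Add beside the second table that its before/after contrast is also affected by time on study and selective retention.

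While editing, reconcile the SAP's statement that the scale was added at all study visits with Table 5:1, which marks it at neither the Entry Visit nor the down-titration call.

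The cost is two small descriptive tables from data already collected and listed, with no hypothesis test. Counts will probably be sparse, so the tables will guide interpretation rather than give precise rates.

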13.3 PCST criteria

13.3.1 Hematology parameters

| Parameter | UCB Conventional Units | SI Units | CF |
|------------------------|---|---|---|
| Hematocrit | For 1 m to < 6 m: ≤ 25% For 6 m to < 2 y: ≤ 27% For 2 y to < 4 y: ≤ 29% For 4 y to < 12 y: ≤ 32% (Female[F]); ≤ 35% (Male [M]) For ≥ 12 y: ≤ 32% (F); ≤ 37% (M) | For 1 m to < 6 m: ≤ 0.25 For 6 m to < 2 y: ≤ 0.27 For 2 y to < 4 y: ≤ 0.29 For 4 y to < 12 y: ≤ 0.32 (F); ≤ 0.35 (M) For ≥ 12 y: ≤ 0.32 (F); ≤ 0.37 (M) | 0.01 |
| Hemoglobin | For < 6 m: ≤ 9.7 g/dL For 6 m to < 12 y: ≤ 10.0 g/dL For ≥ 12 y: ≤ 9.5 g/dL (F); ≤ 11.5 g/dL (M) | For < 6 m: ≤ 97 g/L For 6 m to < 12 y: ≤ 100 g/L For ≥ 12 y: ≤ 95 g/L (F); ≤ 115 g/L (M) | 10 |
| Platelets | ≤ 75 x 10 ⁹ /L or ≥ 700 x 10 ⁹ /L | ≤ 75 x 10 ⁹ /L or ≥ 700 x 10 ⁹ /L | Not applicable (N/A) |
| White Blood Cell (WBC) | For < 17 y: ≤ 3.0 x 10 ⁹ /L or ≥ 20 x 10 ⁹ /L; For ≥ 17 y: ≤ 2.8 x 10 ⁹ /L or ≥ 16 x 10 ⁹ /L; | For < 17 y: ≤ 3.0 x 10 ⁹ /L or ≥ 20 x 10 ⁹ /L; For ≥ 17 y: ≤ 2.8 x 10 ⁹ /L or ≥ 16 x 10 ⁹ /L; | N/A |
| Red Blood Cell (RBC) | For < 17 y: ≤ 2.5 x 10 ⁶ /mm ³ For ≥ 17 y: ≤ 2.0 x 10 ⁶ /mm ³ (F); ≤ 2.5 x 10 ⁶ /mm ³ (M) | For < 17 y: ≤ 2.5 x 10 ¹² /L For ≥ 17 y: ≤ 2.0 x 10 ¹² /L (F); ≤ 2.5 x 10 ¹² /L (M) | 1 |
| Eosinophils | ≥ 10% or ≥ 0.7 x 10 ⁹ /L | ≥ 0.10 or ≥ 0.7 x 10 ⁹ /L | 0.01 or N/A |
| Neutrophils | ≤ 15% or ≤ 1.0 x 10 ⁹ /L | ≤ 0.15 or ≤ 1.0 x 10 ⁹ /L | 0.01 or N/A |
| Basophils | ≥ 5% or ≥ 0.4 x 10 ⁹ /L | ≥ 0.05 or ≥ 0.4 x 10 ⁹ /L | 0.01 or N/A |
| Monocytes | ≥ 20% or ≥ 1.5 x 10 ⁹ /L | ≥ 0.20 or ≥ 1.5 x 10 ⁹ /L | 0.01 or N/A |
| Lymphocytes | For 1 m to < 6 m: ≤ 22% or ≥ 80% ≤ 2.1 x 10 ⁹ /L or ≥ 8.5 x 10 ⁹ /L For 6 m to < 2 y: ≤ 15% or ≥ 80% ≤ 1.5 x 10 ⁹ /L or ≥ 7.5 x 10 ⁹ /L For 2 y to < 12 y: ≤ 12% or ≥ 80% ≤ 1.0 x 10 ⁹ /L or ≥ 7.5 x 10 ⁹ /L For 12 y to < 17 y: ≤ 10% or ≥ 80% ≤ 0.5 x 10 ⁹ /L or ≥ 5.5 x 10 ⁹ /L For ≥ 17 y: ≤ 10% or ≥ 80% ≤ 0.5 x 10 ⁹ /L or ≥ 4.5 x 10 ⁹ /L | For 1 m to < 6 m: ≤ 0.22 or ≥ 0.80 ≤ 2.1 x 10 ⁹ /L or ≥ 8.5 x 10 ⁹ /L For 6 m to < 2 y: ≤ 0.15 or ≥ 0.80 ≤ 1.5 x 10 ⁹ /L or ≥ 7.5 x 10 ⁹ /L For 2 y to < 12 y: ≤ 0.12 or ≥ 0.80 ≤ 1.0 x 10 ⁹ /L or ≥ 7.5 x 10 ⁹ /L For 12 y to < 17 y: ≤ 0.10 or ≥ 0.80 ≤ 0.5 x 10 ⁹ /L or ≥ 5.5 x 10 ⁹ /L For ≥ 17 y: ≤ 0.10 or ≥ 0.80 ≤ 0.5 x 10 ⁹ /L or ≥ 4.5 x 10 ⁹ /L | 0.01 N/A 0.01 N/A 0.01 N/A 0.01 N/A 0.01 N/A |

13.3.2 Blood chemistry parameters

| Parameter | UCB Conventional Units | SI Units | CF |
|-----------------------------|---|---|--------|
| AST (SGOT) | ≥ 3 times of ULN | ≥ 3 times of ULN | N/A |
| ALT (SGPT) | ≥ 3 times of ULN | ≥ 3 times of ULN | N/A |
| ALP | For < 17 y: ≥ 2 times of ULN, if normal range adjusted to the age range; For ≥ 17 y: ≥ 3 times of ULN | For < 17 y: ≥ 2 times of ULN, if normal range adjusted to the age range; For ≥ 17 y: ≥ 3 times of ULN | N/A |
| GGT | ≥ 3 times of ULN, if baseline value ≤ 3 times of ULN | ≥ 3 times of ULN, if baseline value ≤ 3 times of ULN | N/A |
| BUN | ≥ 30 mg/dL | ≥ 10.71 mmol/L | 0.357 |
| Urea | ≥ 60 mg/dL | ≥ 10.02 mmol/L | 0.167 |
| Creatinine | For < 17 y: ≥ 1.5 mg/dL; For ≥ 17 y: ≥ 2.0 mg/dL | For < 17 y: ≥ 132.6 umol/L; For ≥ 17 y: ≥ 176.8 umol/L | 88.4 |
| Creatinine clearance (calc) | For < 12 y: < 70 ml/min (Schwartz) ^(a) For ≥ 12 y: < 70 ml/min (Cockcroft) ^(b) | For < 12 y: < 70 ml/min (Schwartz) ^(a) For ≥ 12 y: < 70 ml/min (Cockcroft) ^(b) | N/A |
| Total bilirubin | ≥ 2.0 mg/dL | ≥ 34.2 umol/L | 17.1 |
| Glucose | ≤ 50 mg/dL or ≥ 180 mg/dL | ≤ 2.775 mmol/L or ≥ 9.99 mmol/L | 0.0555 |
| Total Protein | For ≥ 1 m to < 6 m: ≤ 3.6 g/dL or ≥ 7.8 g/dL For ≥ 6 m to < 17 y: ≤ 4.7 g/dL or ≥ 9.5 g/dL For ≥ 17 y: ≤ 4.5 g/dL or ≥ 9.0 g/dL | For ≥ 1 m to < 6 m: ≤ 36 g/L or ≥ 78 g/L For ≥ 6 m to < 17 y: ≤ 47 g/L or ≥ 95 g/L For ≥ 17 y: ≤ 45 g/L or ≥ 90 g/L | 10 |
| Albumin | For < 17 y: ≤ 2.4 g/dL or ≥ 6.5 g/dL For ≥ 17 y: ≤ 2.5 g/dL or ≥ 6.5 g/dL | For < 17 y: ≤ 24 g/L or ≥ 65 g/L For ≥ 17 y: ≤ 25 g/L or ≥ 65 g/L | 10 |
| Globulin | For < 17 y: ≤ 1.2 g/dL or ≥ 5.0 g/dL For ≥ 17 y: ≤ 1.5 g/dL or ≥ 5.0 g/dL | For < 17 y: ≤ 12 g/L or ≥ 50 g/L For ≥ 17 y: ≤ 15 g/L or ≥ 50 g/L | 10 |
| Sodium | For < 17 y: ≤ 120 mEq/L or ≥ 155 mEq/L For ≥ 17 y: ≤ 115 mEq/L or ≥ 155 mEq/L | For < 17 y: ≤ 120 mmol/L or ≥ 155 mmol/L For ≥ 17 y: ≤ 115 mmol/L or ≥ 155 mmol/L | 1 |
| Potassium | For < 17 y: ≤ 3.0 mEq/L or ≥ 6.5 mEq/L For ≥ 17 y: ≤ 3.0 mEq/L or ≥ 5.8 mEq/L | For < 17 y: ≤ 3.0 mmol/L or ≥ 6.5 mmol/L For ≥ 17 y: ≤ 3.0 mmol/L or ≥ 5.8 mmol/L | 1 |
| Calcium | For < 17 y: ≤ 7 mg/dL or ≥ 11.5 mg/dL For ≥ 17 y: ≤ 7 mg/dL or ≥ 15.5 mg/dL | For < 17 y: ≤ 1.75 mmol/L or ≥ 2.875 mmol/L For ≥ 17 y: ≤ 1.75 mmol/L or ≥ 3.875 mmol/L | 0.25 |

This document cannot be used for marketing authorizations, clinical trial extensions or variations thereof.

| | | | |
|--|---|---|--------|
| Uric Acid | For < 12 y: ≥ 8 mg/dL For ≥ 12 y: ≥ 8 mg/dL (F); ≥ 9.5 mg/dL (M) | For < 12 y: ≥ 475.84 umol/L For ≥ 12 y: ≥ 475.84 umol/L (F); ≥ 565.06 umol/L (M) | 59.48 |
| Cholesterol | ≥ 300 mg/dL | ≥ 7.77 mmol/L | 0.0259 |
| HDL | ≤ 25 mg/dL | ≤ 0.65 mmol/L | 0.0259 |
| LDL | ≥ 200 mg/dL | ≥ 5.18 mmol/L | 0.0259 |
| Triglycerides | ≥ 300 mg/dL | ≥ 3.42 mmol/L | 0.0114 |
| 
^(a) Schwartz equation (patients <12): Cr Cl ml/min = [Height (cm) * 0.55] / serum creatinine
 
^(b) Cockcroft equation (patients ≥12): Male: Cr Cl ml/min = [(140-age) x body weight (kg)] / (72 x serum creatinine), Female: Cr Cl ml/min = [(140-age) x body weight (kg)] / (72 x serum creatinine) x 0.85
 
ALT=alanine aminotransferase; ALP=Alkaline phosphatase; AST=aspartate aminotransferase; BUN=blood urea nitrogen; CR CL=creatinine clearance; GGT=Gamma-glutamyl transpeptidase; HDL=High-density lipoprotein; LDL=low-density lipoprotein; SGOT=serum glutamic oxaloacetic transaminase; SGPT=serum glutamic pyruvic transaminase; ULN=Upper Limit of Normal
 | | | |

This document cannot be used to support any marketing authorization application and any extensions or variations thereof.

13.3.3 Urinalysis

Qualitative urine parameters are generally reported by a descriptive score, which differs among laboratories. For data analysis purpose, a four-point scale is used. Five-point, six-point, or seven-point scales will be collapsed into a four-point scale first. A value is considered possibly clinically significant treatment emergent abnormal if an upward shift of at least 2 degrees from the baseline occurs under investigational treatment. To collapse the results in a five-point scale into a four-point scale, the lowest two positive results will be combined (see example below). For results reported with a scale of more than five-point, please consult your study physician for how to collapse into four-point scale.

| Original Five-point Scale | Four-point Scale |
|---------------------------|--------------------------|
| Negative/None | Negative/None |
| Trace/Rare/Mild/A Few | Trace/1+/Rare/Mild/A Few |
| 1+ | |
| 2+/Mod | 2+/Mod |
| 3+/Sev | 3+/Sev |

13.3.4 Vital signs and body weight

| | |
|------------|---|
| Pulse rate | 
For 1 m to < 12 m: ≤ 110 bpm and a decrease of ≥ 20 bpm from baseline or ≥ 180 bpm and an increase of ≥ 20 bpm from baseline
 
For 12 m to < 3 y: ≤ 90 bpm and a decrease of ≥ 20 bpm from baseline or ≥ 150 bpm and an increase of ≥ 20 bpm from baseline
 
For 3 y to < 12 y: ≤ 65 bpm and a decrease of ≥ 20 bpm from baseline or ≥ 130 bpm and an increase of ≥ 20 bpm from baseline
 
For 12 y to < 17 y: ≤ 60 bpm and a decrease of ≥ 20 bpm from baseline or ≥ 120 bpm and an increase of ≥ 20 bpm from baseline
 
For ≥ 17 y: ≤ 50 bpm and a decrease of ≥ 30 bpm from baseline or ≥ 120 bpm and an increase of ≥ 30 bpm from baseline
 |
|------------|---|

bpm=Beats per minute.

| | |
|--------------------------|---|
| Systolic blood pressure | 
For 1 m to < 12 m: < 60 mmHg and a decrease of > 20 mmHg from baseline or > 110 mmHg and an increase of > 30 mmHg from baseline
 
For 12 m to < 6 y: < 70 mmHg and a decrease of > 20 mmHg from baseline or > 120 mmHg and an increase of > 30 mmHg from baseline
 
For 6 y to < 13 y: < 70 mmHg and a decrease of > 20 mmHg from baseline or > 130 mmHg and an increase of > 30 mmHg from baseline
 
For 13 y and < 17 y: < 90 mmHg and a decrease of > 20 mmHg from baseline or > 140 mmHg and an increase of > 30 mmHg from baseline
 
For ≥ 17 y: < 90 mmHg and a decrease of > 30 mmHg from baseline or > 180 mmHg and an increase of > 40 mmHg from baseline
 |
| Diastolic blood pressure | 
For 1 m to < 12 m: < 40 mmHg and a decrease of > 15 mmHg from baseline or > 60 mmHg and an increase of > 20 mmHg from baseline
 
For 12 m to < 6 y: < 45 mmHg and a decrease of > 15 mmHg from baseline or > 80 mmHg and an increase of > 20 mmHg from baseline
 
For 6 y to < 13 y: < 50 mmHg and a decrease of > 15 mmHg from baseline or > 85 mmHg and an increase of > 20 mmHg from baseline
 
For 13 y to < 17 y: < 55 mmHg and a decrease of > 20 mmHg from baseline or > 90 mmHg and an increase of > 30 mmHg from baseline
 
For ≥ 17 y: < 50 mmHg and a decrease of > 20 mmHg from baseline or > 105 mmHg and an increase of > 30 mmHg from baseline
 |
| Weight | 
For < 17 y: < 3% or > 97% of the normal body weight growth curve ranges for the age at date of weight assessment ^(a) and gender;
 
For ≥ 17 y: change of ≥ 7% of baseline weight
 |

^(a) Once the subject reaches 17 years of age use the body curve criteria of a 17 year old regardless of their age in the study.

